6.1.2. Medical History

For Medical History, medical condition or event terms will be coded using the Medical Dictionary for Regulatory Activities (MedDRA).

The number and percentage of participants with any Pre-Existing Conditions and Medical History will be summarized overall and for each system organ class and preferred term. Participant Pre-Existing Conditions and Medical History data including specific details will be presented in a listing.

General Associated Person Medical History data will be listed for each participant. The number and percentage of participants having first degree relative with medical history will be summarized overall and for each system organ class and preferred term.

Associated Person Medical History data for Liver Disease will also be listed and the number (percentage) of participants associated with a certain medical condition or event (Alpha-1 antitrypsin Deficiency, Autoimmune disorder, Hemochromatosis) will be summarized by preferred term.

Prespecified Medical History including the date of diabetes diagnosis, Liver and Concurrent Disease will be listed. The number and percentage of participants with any Liver and Concurrent Disease will be summarized overall and for each system organ class and preferred term.

Percentages will be calculated based on number of participants in the mITT set.

6.2. Appendix 2: Treatment Compliance

Participants should administer Tirzepatide once weekly by SC injection.

Treatment overdose is defined as administration of more than a total of 3 SDPs (15mg) of Tirzepatid within a 72-hour period. If a dose is missed, the participant should take their dose as soon as possible, within 4 days (96 hours) after the missed dose. If more than 4 days have passed, that dose should be skipped, and the next dose should be taken at the appropriate time.

For each participant, study treatment compliance will be determined for each week by taking into account whether a participant takes all doses of study treatment as instructed based on the subject diary. If on a given week a participant overdosed treatment or a dose had to be skipped then that will count as non-compliance for that week. Weekly compliance along with weekly actual dose and skipped doses will be listed for each participant. Number and percentage of participants who were compliant, non-compliant (due to overdosing or due to skipping dose) will be summarized by week.

Furthermore, compliance will be characterized by accountability data for each visit. The number of SC injections taken will be calculated by subtracting the number of SDPs returned from the number of SDPs dispensed at a visit.

The study intervention compliance (%) for each visit will be calculated by dividing the total number of SDPs used up to the next visit by the total number of SDPs prescribed at each visit and then multiplying by 100. The overall study intervention compliance (%) will be calculated by dividing the total number of SDPs used at all visits by the total number of SDPs prescribed for all visits and then multiplying by 100.

Compliance (%) = [(total number of SDPs dispensed – total number of unused SDPs returned) / (Number of weeks in visit interval × Number of SDPs prescribed per week)] × 100.

Treatment compliance will be summarized descriptively. Furthermore, for overall compliance a categorical summary of whether participants were compliant (yes/no) will be presented. A participant is considered compliant if overall study intervention compliance is greater than or equal to 75%.

Percentages will be calculated out of the number of participants who were dosed at that dosing period in the Safety set.

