#### 6.5.1. Management of Participants with Gastrointestinal Symptoms

The dose scheme is designed to assess the glycemic transition from a GLP-1 RA directly to 5 mg and assess the development of intolerable GI symptoms. Every effort should be made by the investigator to maintain the 5 mg dose throughout the trial.

This table describes steps the investigator should follow to mitigate GI symptoms and manage participants with intolerable GI AEs.

STEP 1	Advise participants to eat smaller meals, for example, splitting 3 daily meals into 4 or more smaller meals, and to stop eating when they feel full.
STEP 2	Continue STEP 1 + Prescribe symptomatic medication, for example, anti-emetic or anti-diarrheal medication, per local country availability and individual participant needs. Use of symptomatic medication should be captured as concomitant medication in the CRF.

STEP 3	Continue STEP 1 + STEP 2 + Temporarily interrupt tirzepatide; omit 1 dose. After the interruption, the investigator should restart tirzepatide 5 mg, with the participant taking medication to alleviate their GI symptoms. The data related to temporary interruption of study treatment should be documented in source documents.
	during the 12-week study, each with an attempt to restart the subsequent dose.
STEP 4	If intolerable GI symptoms or events persist despite the above measures, the investigator may discontinue study drug intervention.

Abbreviations: CRF = case report form; GI = gastrointestinal.

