# Recording temporary discontinuation of tirzepatide

The dates of study intervention interruption and restart must be documented in source documents and entered on the CRF.

Participant noncompliance should not be recorded as interruption of study intervention on the CRF.

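### SAP 6.2 has no category for investigator-directed interruptions, so its compliance summaries mix protocol-directed omissions with missed doses, and no planned table counts interruptions for GI symptoms

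*SAP*

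**What the plan says.** **SAP 6.2.** Weekly compliance comes from the participant diary and is first described as taking doses the way the participant was told to. The next sentence sets the rule: a week with an overdose is non-compliant, and so is one where "a dose had to be skipped then that will count as non-compliance for that week". Two outputs follow: "Number and percentage of participants who were compliant, non-compliant (due to overdosing or due to skipping dose) will be summarized by week", and "Weekly compliance along with weekly actual dose and skipped doses will be listed for each participant". A second measure uses pen accountability: pens dispensed minus unused pens returned, divided by weeks in the visit interval times pens prescribed per week. It is dichotomised overall: "A participant is considered compliant if overall study intervention compliance is greater than or equal to 75" percent.

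**Protocol 6.5.1, Step 3 (GI symptoms).** The investigator's instruction is "Temporarily interrupt tirzepatide; omit 1 dose". Step 3 adds: "The data related to temporary interruption of study treatment should be documented in source documents".

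**Protocol 7.1.1 and 7.1.2.** Section 7.1.1 sets liver-test conditions under which study drug is interrupted. Section 7.1.2 lists further reasons for a temporary stop and, on recording, says: "The dates of study intervention interruption and restart must be documented in source documents and entered on the CRF". It also says: "Participant noncompliance should not be recorded as interruption of study intervention on the CRF".

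**The concern.** The protocol treats a directed interruption and participant non-compliance as two different things and collects them separately. SAP 6.2 has one bin for both. A participant who does exactly what the investigator says under Step 3 has that week scored non-compliant for skipping a dose, and loses accountability percentage as well.

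This matters because describing GI tolerability of a direct start at 5 mg is a stated purpose (Protocol 1.1 Rationale and 4.2). How many participants could not stay on weekly dosing without an interruption is a plain readout of that purpose. The data are required on the CRF, but the SAP plans no summary of them, and the compliance table cannot stand in because it does not give the reason for a skip.

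**Working it through.** **1. Does any other planned output recover the information?**

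| SAP section | What it covers | Interruptions shown? |
|---|---|---|
| 4.1 intercurrent events | Treatment discontinuation; prohibited medication | No |
| 4.2 disposition | Permanent discontinuation, with reasons | No |
| 4.6.1 exposure | First to last dose; missed doses ignored | No |
| 4.6.2 AE action taken | Drug Withdrawn only | No |
| 4.6.4.4 GI events | Type, severity, duration, time course | No |
| 6.2 compliance | Weekly count of skips; listing of skipped doses | Yes, but not by reason |

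A skip can be seen; its reason cannot.

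**2. Effect on accountability compliance.** Inputs: weekly dosing (Protocol 6.1) for 12 weeks (Protocol 4.2), read as 12 planned doses; visits at Weeks 0, 4, 8 and 12 (Schedule of Activities), so nominal 4-week intervals; threshold 75% (SAP 6.2). With k omitted doses and no other deviation, overall compliance is (12 − k)/12:

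- k = 1: 11/12 = 91.7%, compliant
- k = 2: 10/12 = 83.3%, compliant
- k = 3: 9/12 = 75.0%, compliant (the rule includes equality)
- k = 4: 8/12 = 66.7%, non-compliant

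Within one 4-week interval, compliance is (4 − k)/4: one omission gives 3/4 = 75%, two give 2/4 = 50%.

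If directed omissions left the denominator, one Step 3 omission would give 11/11 = 100% overall and 3/3 = 100% in the interval.

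**3. Effect on the weekly table.** The interruption rate is not in the documents. Assume that a fraction p of the 150 participants each omit one dose on instruction. Total participant-weeks: 150 × 12 = 1800. Mislabelled share: p × 150 / 1800 = p/12.

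- p = 5%: 7.5/1800 = 0.4%
- p = 10%: 15/1800 = 0.8%
- p = 20%: 30/1800 = 1.7%

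This uses a fixed denominator of 150. SAP 6.2 instead takes percentages out of participants dosed in the period. Read literally, that could drop a person who skipped the week from the denominator, so the wording needs tidying in any case.

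**The case against.** **The rule may mean something narrower.** The sentence comes after the missed-dose rule, under which a dose more than 4 days late is skipped. It could refer only to those doses, and the preceding test of following instructions would then protect a Step 3 omission. This is a fair reading, but the SAP does not state it, and two programmers could classify the same week differently. It also does not help the accountability percentage, whose denominator makes no allowance for directed weeks.

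**The recording rule runs one way.** Section 7.1.2 bars entering non-compliance as an interruption; it does not forbid an interrupted week from lowering a doses-taken measure. That is correct. It still shows that the protocol separates the two and that the data to do so are required.

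**GI intolerance is reported elsewhere.** A reader might infer that intolerance is reported as poor adherence, or understated. The documents do not support that. GI events appear in the treatment-emergent AE tables, in discontinuations due to AEs and in SAP 4.6.4.4. Nor are skipped doses invisible, since they have their own weekly count and a listing. What is absent is the reason, and a count of GI-related interruptions.

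**The two recording sentences can both be followed.** Step 3 names source documents but does not say only those; 7.1.2 adds the CRF. This is not a contradiction, although a site reading Step 3 alone could overlook the CRF entry.

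**The table shells are in a separate document** (SAP Introduction) and might contain more. They should implement the SAP rule, though, and the rule has no such category.

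**Conclusion.** The point holds as a gap in descriptive reporting. SAP 6.2 merges directed interruptions with participant misses, against a distinction that the protocol draws, and no planned table shows how many participants needed an interruption for GI symptoms.

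The size is modest: 0.4% to 1.7% of participant-weeks mislabelled if 5% to 20% of participants omit one dose each. That rate is an assumption, and the share rises in proportion if participants omit more.

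Three stronger conclusions should not be drawn:

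- **That compliant participants will fail the overall flag.** It changes only at a fourth omission. The Step 3 sentence on the number of interruptions is incomplete in the available text, so whether Step 3 alone can lead there cannot be determined.
- **That the mislabelling clusters in particular weeks.** The documents give no weekly timing of GI events within the treatment period.
- **That efficacy results are affected.** A temporary interruption is not an intercurrent event, its data stay in the Efficacy Analysis Set, and compliance defines no analysis set. The primary HbA1c analysis is untouched.

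**What to change.** Change the SAP only:

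- **6.2, weekly table.** Use the CRF interruption and restart dates to divide weeks without a dose into directed interruption (by reason: GI AE, liver test, other) and dose missed by the participant. Count only the second as non-compliance. State the denominator so that a participant who skipped a week remains in it.
- **6.2, accountability.** Show compliance with and without directed omissions in the denominator.
- **4.6.4.4.** Add the number and percentage of participants with at least one interruption for a GI AE, and the number of doses omitted.

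Optionally, add a cross-reference from Protocol 6.5.1 Step 3 to 7.1.2 so that the CRF entry is clear. No dose or clinical rule changes.

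The cost is a few sentences and one extra table, from data that 7.1.2 already requires. The limitation is reliance on sites coding the reason correctly: an interruption entered as participant choice, or the reverse, would remain misclassified.

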Dosing							
Register visit with IWRS	Х	Х	Х	Х	Х	Х	
Dispense study intervention using IWRS		Х	Х	Х			
Observe participant administer study intervention		Х					
Dispense ancillary supplies to participant		Х	Х	Х			
Participant returns unused study intervention and ancillary supplies			Х	Х	Х	Х	Where applicable as per local regulations.
Assess study intervention compliance			Х	Х	Х	Х	

Investigator; SoA = Schedule of Activities; SMBG = self-monitoring of blood glucose; T2D = Type 2 diabetes; WOCBP = women of childbearing potential. Abbreviations: BG = blood glucose; CKD-EPI = chronic kidney disease - epidemiology collaboration; CGM = continuous glucose monitoring; CRF = case report form; ECG = electrocardiogram; GLP-1 RA = glucagon-like peptide-1 receptor agonist; IWRS = interactive web-response system; PI = Principal

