### First tirzepatide dose

Study personnel will observe as the participant injects the first dose of tirzepatide. The remaining injections will occur at participant's home. The date and time of the first dose of tirzepatide should be recorded on the CRF. Additionally, all medication doses administered at home should be captured, including date and time, in the participant's diary and subsequently recorded in the CRF.

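### Overall compliance and its 75% flag count every pen not returned as injected, although returns depend on local rules and each dose is already recorded in the diary and CRF

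*SAP*

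**What the plan says.** SAP Section 6.2 (Appendix 2) defines two measures.

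- **Weekly, from the diary.** A week with a skipped dose or an overdose is non-compliant. Results are listed by participant and tabulated by week.
- **By visit and overall, from pen accountability.** The SAP states: "The number of SC injections taken will be calculated by subtracting the number of SDPs returned from the number of SDPs dispensed at a visit". Its displayed formula has as numerator "total number of SDPs dispensed – total number of unused SDPs returned" and as denominator "Number of weeks in visit interval × Number of SDPs prescribed per week". The overall figure comes from "dividing the total number of SDPs used at all visits by the total number of SDPs prescribed for all visits".

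The yes/no classification uses the second measure only: "A participant is considered compliant if overall study intervention compliance is greater than or equal to 75" per cent.

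The Dosing rows of the Schedule of Activities (Protocol Section 1.3) include "Participant returns unused study intervention and ancillary supplies" at Visits 3, 4, 5 and early discontinuation, with the comment "Where applicable as per local regulations".

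The protocol also records doses directly. After the observed first injection, "all medication doses administered at home should be captured, including date and time", in the diary and then in the CRF (Protocol Section 4.1.1). Protocol Section 6.4 has site staff assess compliance from returned pens together with what the participant reports about injections.

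**The concern.** The pen count has no term for a pen that was neither injected nor returned, so that pen is treated as injected. Such pens are foreseeable in a multinational trial where returns depend on local regulations. They can also arise through loss to follow-up, or where Protocol Section 10.8 lets participants be told how to dispose of unused supplies themselves.

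With the denominator held fixed, each such pen can only raise the score. The overall measure and the 75% flag are then least able to detect non-adherence where returns are least complete. For the same participant, the flag could say compliant while the weekly diary table shows missed doses, and the SAP does not say which prevails.

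The adherence summary has a real job here. The efficacy analysis set drops data only after permanent discontinuation or prohibited medication, so data from participants who merely skip doses stay in. Exposure (SAP Section 4.6.1) ignores missed doses, and Protocol Section 7.1.2 says non-compliance is not to be recorded as an interruption. Readers would look to the compliance figures to learn how fully the 5 mg weekly regimen was taken.

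**Working it through.** The SAP states no compliance result to reproduce; 75% is a chosen threshold. The check is to evaluate the SAP formula directly.

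**Inputs**
- One pen per injection, one injection per week, 12 weeks: 12 doses due (Protocol Sections 6.1, 6.1.1 and 4.2).
- Pens dispensed at Visits 2, 3 and 4 (Schedule of Activities). The number per visit is not given. Assumed 4, so 12 in total; 5 and 6 are checked below.
- Share of unused pens returned: 100%, 50% or 0%, as illustrations.

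**Formula**

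Score = 100 × (dispensed − unused returned) / (weeks × 1). True compliance = 100 × injections / 12.

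For 6 injections, 6 pens are unused:
- all returned: (12 − 6)/12 = 50.0%
- half returned: (12 − 3)/12 = 75.0%
- none returned: (12 − 0)/12 = 100.0%

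| Injections of 12 | True % | All unused returned | Half returned | None returned |
|---|---|---|---|---|
| 1 | 8.3 | 8.3 | 54.2 | 100.0 |
| 4 | 33.3 | 33.3 | 66.7 | 100.0 |
| 6 | 50.0 | 50.0 | 75.0 | 100.0 |
| 8 | 66.7 | 66.7 | 83.3 | 100.0 |
| 9 | 75.0 | 75.0 | 87.5 | 100.0 |

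With full return the score equals the truth. With half returned, 6 and 8 injections cross 75% wrongly, while 1 and 4 are still flagged. With none returned, everyone is compliant. In general the score falls below 75% only if 12 − returned < 9, that is, if at least 4 unused pens come back.

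**Participants lost early (no pens returned)**

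The result depends on a denominator that the SAP does not specify.
- Lost after Visit 2, 4 pens kept: 4/4 = 100% if only dispensed intervals count; 4/12 = 33.3% if all 12 planned weeks count.
- Lost after Visit 3, 8 pens kept: 8/8 = 100% or 8/12 = 66.7%. If 4 or 5 of the 8 were injected, the truth over the dispensed interval is 4/8 = 50% or 5/8 = 62.5%.
- Lost after Visit 4, 12 pens dispensed and none returned: 12/12 = 100% on either reading.

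**Sensitivity to the assumptions**
- 5 or 6 pens per 4 weeks, none returned: 5/4 = 125% or 6/4 = 150%.
- 4 pens with an actual interval of 25 or 31 days: 4/(25/7) = 112.0% or 4/(31/7) = 90.3%.
- The prose subtracts all pens returned, the formula only unused ones. Read literally, the prose gives (12 − 12)/12 = 0% for a fully adherent participant who hands back 12 used pens.

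**The case against.** The strongest reply is that the SAP does not rely on the pen count alone. Diary-based weekly compliance comes first in the same section, skipped doses are listed for each participant, and the pen count is a second view. Permanent discontinuation also appears in the disposition and intercurrent-event tables. This stands: a reader might infer that missed injections go unseen, and the documents do not support that. It does not rescue the overall figure or the flag, because neither draws on the diary.

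A reader might also infer that every non-adherent or lost participant scores 100%. The documents do not support that either. Participants who return their unused pens are scored correctly, and partial return gives intermediate scores. Loss after Visit 2 or Visit 3 gives 100% only if the denominator stops at the dispensed intervals.

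The return condition does not show that any participating country bars returns. Protocol Section 6.2 requires reconciliation and final disposition records and refers to a Pharmacy Manual that is not among the documents. The frequency of unreturned pens is therefore unknown.

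Nor is every error upward: a long visit interval or returned used pens can lower the score. The upward direction applies to unreturned, uninjected pens with the denominator fixed.

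Finally, the diary is self-reported on paper, and the last one may be missing for the same lost participants whose pens are missing. That is a real limit on the remedy.

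**Conclusion.** The point holds in a limited form. Overall compliance and the 75% flag rest on a stated rule that credits any pen neither returned nor injected. Where unused pens are not returned, a participant can score up to 100% and be labelled compliant whatever was injected, in conflict with the diary table. The worked case, 6 of 12 injections scored 100% against a true 50%, assumes 4 pens per interval, nominal 4-week intervals and no returns.

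The number affected cannot be estimated from the documents. The consequence is confined to a descriptive adherence summary. A reader might fear for the primary result, but compliance neither defines the efficacy analysis set nor enters the primary repeated-measures model. It is still worth correcting: the rule can misclassify participants, and the data for a better one are already collected.

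**What to change.** In SAP Section 6.2:

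1. Derive overall compliance and the 75% flag from injections recorded in the diary and CRF, divided by weekly doses due.
2. State the denominator for participants who stop early or are lost: doses due while on treatment, or all 12 planned. Label the table accordingly.
3. Keep the pen count as a cross-check, and make its prose match its formula so that only unused pens are subtracted.
4. Report pens neither returned nor recorded as injected in a separate unaccounted-for category, not as taken.

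With complete records, 1, 4, 6, 8 and 9 injections of 12 would give 8.3%, 33.3%, 50.0%, 66.7% and 75.0%, and only the last would meet the threshold, regardless of pen returns.

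The cost is a wording change and a different numerator; no new data are needed. Because diary data are self-reported and a final diary may be missing, reported compliance may be slightly lower or partly unknown.

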6.3. Appendix 3: Search Criteria for Standardized MedDRA Queries

The Standardized MedDRA Queries of interest are listed as follows:

- Systemic hypersensitivity and anaphylactic reactions:
 - Anaphylactic reaction (SMQ), narrow search
 - Hypersensitivity (SMQ), narrow search
 - Angioedema (SMQ), narrow search
 - Severe cutaneous adverse reactions (SMQ), narrow search
- Hepatic disorders (SMQ)
- Gallbladder related disorders (SMQ)
- Acute pancreatitis (SMQ)
- Cardiac arrythmias (SMQ)

CONFIDENTIAL

• Biliary disorders (SMQ)

The search criteria for each of the SMQs are stored in PPD Biostatistics Technology Infrastructure (BTI) in:

\\wilbtib\wilbtia00\Global Bios Library\Dictionaries\MedDRA\Current\MedAscii\smq_list.asc

7. References

